5.2.4. Logistic Regression

The logistic regression model(s) will include a term for treatment, strata (females versus males), and baseline will be included as a covariate.

Missing values (e.g. due to censoring) will be imputed for missing data using a multiple imputation method as described in Section 5.3.

The odds ratio for each treatment group of danuglipron relative to placebo and corresponding 90% confidence interval will be obtained.

Example SAS code is provided in Appendix 3.

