Measurements after discontinuation of study intervention will be censored and treated as missing data. Missing data due to censoring, study withdrawal, or other reasons (eg, laboratory failure) may be imputed as outlined in the SAP. The population-based treatment effect will be the odds of achieving a body weight loss ≥5% from baseline at End of Treatment on PF-06882961 compared to the odds of achieving this on placebo (ie, odds ratio).

Estimands related to other endpoints:

Estimand 3 is similar to Estimand 1, except the population average treatment effect is on the absolute CFB in waist circumference at End of Treatment. The population based treatment effect will be the mean CFB in each PF-06882961 arm compared to placebo.

Estimands 4, 5 and 6 will utilize the same approach as Estimand 3 for the associated endpoint(s).

Tertiary endpoints may be analyzed using similar estimands or analyzed in a descriptive manner without reference to an estimand. Other supporting estimands may be used for some of the primary and secondary endpoints as a means to examine the robustness of results, compare to available literature and/or be used for future study planning as needed. Details of these estimands and analyses will be presented in the SAP.

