2.2.2. Secondary Estimand(s)

2.2.2.1. Estimand related to achieving Body Weight loss ≥5% at End of Treatment

A secondary estimand (Estimand 2) will be the population odds ratio of the treatment effect of achieving a body weight loss \geq 5% from baseline at End of Treatment of PF-06882961 (danuglipron) compared to placebo in all evaluable participants while on treatment. This reflects a combination of the 'Hypothetical' and 'While on treatment' strategies as outlined in the ICH-E9 (R1) guidance.¹ It includes the following 4 attributes:

Population: Defined by the inclusion and exclusion criteria to reflect participants with obesity

PFIZER CONFIDENTIAL DMB02-GSOP-RF02 8.0 *Statistical Analysis Plan Template* TMF Doc ID: 98.03 Page 11 of 61

- Variable: Response as defined by a body weight loss of ≥5% from baseline at End of Treatment
- Intercurrent events: All data after an intercurrent event of discontinuation of investigational product (IP) will be censored. Missing or censored values at End of Treatment will be imputed (assuming missing at random [MAR]) to determine a response classification.
- Population-level summary: Odds ratio for a response between danuglipron (each arm considered separately) and placebo

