5.3.1. Multiple Imputation

For summarizing the proportion of responses in body weight, all data from Estimand Set 1 will be included (i.e. all time points up to and including End of Treatment). A multiple imputation (MI) method will be implemented, using a multivariate imputation method by chained equations, which is still valid with an arbitrary missing data pattern. The model will include: treatment, baseline body weight and strata. Twenty sets of imputations of each missing value will be constructed from the MI method and the proportion of responses by treatment group will be determined with associated standard errors utilizing a normal approximation and will be combined using standard multiple imputation techniques proposed by Rubin⁸ to yield overall estimates. If there is more missing data in the study than anticipated, the number of imputation sets may be increased as required.

For logistic regression of body weight, all data from Estimand Set 1 will be included (i.e. all time points up to and including End of Treatment). The same imputed datasets as produced for the proportion of responses above will be utilized, where a Logistic Regression model (as described in Section 5.2.4) will be applied to each of the 20 imputed datasets separately. Parameter estimates of the log odds ratios for each treatment group relative to placebo will be combined using standard multiple imputation techniques proposed by Rubin⁸ to yield overall estimates of the log odds ratios and their associated standard errors will be used to create 90% confidence intervals on the log-odds scale. The log odds ratios and log odds 90% confidence intervals will be back transformed into odds ratios and associated 90% confidence intervals for final reporting.

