PFIZER CONFIDENTIAL DMB02-GSOP-RF02 8.0 *Statistical Analysis Plan Template* TMF Doc ID: 98.03 Page 52 of 61

```
merge prop_mi_0 prop_mi_1;
by _imputation_ treatment;
total = count_0 + count_1;
p = count_1/total;
q = count_0/total;
se_p = sqrt((p*q)/total);
```

run;

```
proc sort data=prop_mi_combined;
by treatment _imputation_;
proc mianalyze data=prop_mi_combined alpha=0.1;
by treatment;
modeleffects p;
stderr se_p;
ods output parameterestimates=prop_mi_out;
run;
```

Example SAS code for Logistic Regression Model (with multiple imputation):

The same imputed datasets as produced above for the 'Proportion of Responses' will be utilized. Note: the imputed dataset should be ordered so that the group 'Placebo' and 'Resp'=1 comes first to ensure that the reference group is Placebo and the odds ratios are for a response = 1.

```
* Fit logistic regressions to each imputed dataset and combine results;
proc sort data=analysis_mi_26;
        by _imputation_ descending treatment descending resp;
proc logistic data = analysis mi 26 order=data;
       by imputation ;
       class resp treatment strata;
       model resp = treatment strata base/alpha=0.1;
       oddsratio dose/diff=all:
       ods output OddsRatiosWald=OddsRatiosWald mi;
run;
data OddsRatiosWald mi;
       set OddsRatiosWald mi;
       if effect = . then delete;
       estimate = log(OddsRatioEst);
       SE = (log(UpperCL) - log(LowerCL))/(2*QUANTILE('NORMAL',0.95));
run:
proc sort data=OddsRatiosWald mi;
       by effect imputation ;
proc mianalyze data=OddsRatiosWald mi alpha=0.1;
```

```
by effect;
modeleffects estimate;
stderr SE;
ods output parameterestimates=OddsRatiosWald_mi_out;
```

run;

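### Estimand 2 is worded as a population odds ratio, but the planned logistic regression reports an odds ratio conditional on sex and baseline weight, with no step to connect the two

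*SAP*

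**What the plan says.** **Estimand.** SAP 2.2.2.1 states that Estimand 2 "will be the population odds ratio of the treatment effect of" achieving the 5% loss. Its summary attribute reads: "Population-level summary: Odds ratio for a response between danuglipron (each arm considered separately) and placebo". Protocol 9.1 spells out the contrast: "The population-based treatment effect will be the odds of achieving a body weight loss ≥5% from baseline at End of Treatment on PF-06882961", set against the corresponding odds on placebo. None of these passages conditions on a covariate.

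**Estimator.** SAP 5.2.4 specifies the model: "The logistic regression model(s) will include a term for treatment, strata (females versus males), and baseline will be included as a covariate". Protocol 9.4.1.2 and 9.4.3 and SAP 6.2.1 agree, and they name this model as the one that estimates Estimand 2. The example code in SAP Appendix 3 is "model resp = treatment strata base/alpha=0.1". SAP 5.3.1 then says: "Parameter estimates of the log odds ratios for each treatment group relative to placebo will be combined using standard multiple imputation techniques". The pooled values are back-transformed for reporting.

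**Also planned.** SAP 5.3.1 and 6.2.1 report the response proportion in each arm after multiple imputation. No odds ratio is formed from those proportions.

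**The concern.** The exponentiated treatment coefficient from a main-effects logistic model compares two people of the same sex and baseline weight. The estimand text compares the odds of response in the whole population under drug with the odds in the whole population under placebo. For a mean difference from a linear model without a treatment-by-covariate interaction the distinction disappears. For an odds ratio it does not, even under perfect randomisation, once the covariates predict response and treatment has an effect.

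The responder result would then carry the label of one quantity and the value of another. A reader who computes the odds ratio from the imputed response proportions would generally get a different number, with nothing in the SAP to explain why. The gap grows with the treatment effect, so it would be largest for the most effective arms.

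**Working it through.** **No figure to reproduce.** The documents give no odds ratio, response rate or covariate effect for this endpoint. The calculations below rest on anchors and assumptions.

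**Anchors.** From SAP Appendix 2: SD of the log weight ratio 0.068 (example value in the code) and a 200 mg versus placebo log difference of -0.067 (prior mean). From SAP Appendix 3: response means a log ratio below ln(0.95) = -0.0513. From Protocol 4.1: at most about 70% of one sex, so 50% and 70% are used. *Assumed:* placebo mean log change 0, normal log ratios, and the covariate effects shown below.

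**Step 1: implied marginal odds ratio.**
- Placebo: Φ(-0.0513/0.068) = Φ(-0.754) = 22.5%.
- Drug: Φ((-0.0513 + 0.067)/0.068) = Φ(0.231) = 59.1%.
- Odds ratio: (0.591/0.409)/(0.225/0.775) = 4.98.
- With a smaller log difference of -0.0356, the rates are 22.5% and 40.9% and the odds ratio is 2.38. That value is (1.645 + 0.842) × 0.068 × √(2/45), the difference detectable with 80% power for 45 versus 45 at one-sided 5%.

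**Step 2: the mechanism by hand.** Take equal numbers of each sex, a sex odds ratio of 2 and no weight effect. Let placebo odds be 0.2 and 0.4, with a conditional treatment odds ratio of 5.
- Placebo rates are 16.7% and 28.6%, mean 22.6%.
- Drug odds are 1 and 2, so rates are 50.0% and 66.7%, mean 58.3%.
- Marginal odds ratio: (0.583/0.417)/(0.226/0.774) = 1.400/0.292 = 4.79.
- Conditional over marginal: 5/4.79 = 1.04.

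**Step 3: sex and baseline weight together.** A main-effects logistic model was integrated over sex and a standard-normal baseline weight. It was solved for the conditional odds ratio that gives the marginal rates in Step 1. Ranges cover 50% to 70% of one sex.

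| Sex OR; weight OR per SD | Conditional OR (marginal 4.98) | Ratio | Ratio (marginal 2.38) |
|---|---|---|---|
| 1; 1 | 4.98 | 1.00 | 1.00 |
| 1.2; 1.1 | 5.01 | 1.01 | 1.00 |
| 1.5; 1.2 | 5.10-5.11 | 1.02-1.03 | 1.01 |
| 2; 1.3 | 5.28-5.33 | 1.06-1.07 | 1.03-1.04 |
| 2; 1.5 | 5.45-5.50 | 1.10-1.11 | 1.05 |
| 3; 2 | 6.30-6.44 | 1.27-1.30 | 1.13-1.14 |

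For a larger effect (10% versus 50%, marginal 9.0), the row 2; 1.5 gives 1.10-1.12 and the row 3; 2 gives 1.30-1.34. With equal response rates in the two arms the conditional odds ratio is 1.

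**Step 4: cross-checks.**
- Logistic fits to simulated normal log ratios, with the two covariates explaining 2%, 5%, 10% and 20% of within-arm variance, give ratios of 1.02, 1.05, 1.12 and 1.26 at -0.067, and 1.01, 1.03, 1.06 and 1.13 at -0.0356.
- A separate set of assumptions (65% women, placebo response 10-20%, sex log-odds 0.4-1.0, weight log-odds 0.1-0.4 per SD) maps a conditional 4 to a marginal 3.63-3.96 and a conditional 10 to 8.41-9.81. The ratios are 4/3.96 = 1.01 to 4/3.63 = 1.10, and 10/9.81 = 1.02 to 10/8.41 = 1.19.

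**Step 5: against sampling error.** SE of the log odds ratio = √[1/(n0 p0(1-p0)) + 1/(n1 p1(1-p1))], with rates from Step 1 and no missing data:
- 67 versus 60: √(1/11.68 + 1/14.50) = 0.39, 90% CI factor exp(1.645 × 0.393) = 1.91.
- 67 versus 34: 0.46, factor 2.11.
- Cohort 3, 16 versus 32: 0.70, factor 3.15.

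A ratio of 1.11 is a shift of about 0.10 in the log odds ratio, roughly a quarter of the smallest of these SEs.

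**The case against.** The best defence is that the documents never use the word marginal. Population is generic estimand vocabulary in this SAP, and both documents openly name the adjusted model as the analysis for Estimand 2. A conditional odds ratio is a legitimate target and not a biased estimate of anything. The arm-level proportions after imputation are also reported, so a reader can form the marginal odds ratio.

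Part of this stands. The adjusted model is disclosed and valid, and the proportions mitigate the problem. But Protocol 9.1 defines the effect as odds on drug against odds on placebo with no conditioning, and the arm-level reading is the natural one. Disclosing an estimator does not make it estimate the quantity named.

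Two stronger readings are tempting, and the documents support neither.
- *The reported odds ratio will overstate the estimand.* That needs a real effect, prognostic covariates and no treatment-by-covariate interaction. Protocol 4.1 says only that efficacy may differ by sex. Response is already expressed relative to baseline weight, so strong dependence on that weight cannot be presumed. SAP 5.2.6 itself entertains a baseline-by-dose interaction. Even where the conditions held, in 2,000 simulated trials of 67 versus 60 the adjusted odds ratio was further from 1 than the crude one in 80% (covariates explaining 5% of variance) to 86% (10%), not in all.
- *Dose selection is distorted because the gap is largest for the best arms.* Over one covariate distribution in a main-effects model the marginal odds ratio rises with the conditional one, so arms keep their order. The dose-response models in SAP 5.2.5 and 5.2.6 use body-weight means, not responder odds ratios.

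**Conclusion.** The mismatch is real: the plan names a population odds ratio, reports a conditional one, and has no step between them. With a non-null effect, predictive covariates and no interaction, the reported value tends to lie further from 1 than the stated estimand.

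The likely size is modest. For weak to moderate covariates (sex odds ratio up to 2, weight odds ratio up to 1.5 per SD) the gap is roughly 0-11% at a marginal odds ratio near 5, and at most about 5% near 2.4. Gaps approaching 20% or more need strong covariates, very large treatment effects, or both. Every figure depends on covariate effects and a placebo response that the documents do not give.

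The gap is small beside the 90% confidence intervals and zero at the null, so a test of no effect is not distorted. SAP 5.1 bases inference on the primary endpoint. Although its opening sentence mentions testing efficacy-related secondary endpoints, it closes by excluding formal tests beyond the primary. This concerns the meaning of one secondary estimate, not the trial's primary conclusion.

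**What to change.** Keep the logistic model and the imputations, and add a standardisation step to SAP 5.2.4, 5.3.1 and Appendix 3:

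1. In each imputed dataset, fit the planned model.
2. Predict response for every participant in the analysis set with treatment set to each arm in turn, and average the predictions by arm. Do this separately for Cohorts 1 and 2 combined and for Cohort 3.
3. Form the log odds ratio of each arm's average against placebo, with a delta-method or bootstrap standard error.
4. Pool by Rubin's rules, back-transform, and report the result with its 90% confidence interval as the Estimand 2 estimate.
5. Retain the covariate-adjusted odds ratio alongside, labelled as conditional on sex and baseline weight.

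Redefining Estimand 2 as conditional on sex and baseline weight would also remove the mismatch, but it changes the quantity the protocol names. Standardisation leaves the protocol as written.

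The cost is a short extra analysis step and possibly a slightly less favourable odds ratio. No new data are needed.

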5.2.5. Emax Model

The 4-parameter dose-response Emax model will be used to characterize the percent change from baseline (%CFB) dose-response relationships with dose included as a continuous variable.

The model structure will take the form:

$$log_e CFB = log_e(E_0) + \frac{log_e(E_{max}) \times dose^{Hill}}{ED_{50}^{Hill} + dose^{Hill}}$$

 E_0 is the placebo effect, *dose* is the target randomized dose, E_{max} is the maximum effect, ED_{50} is the dose producing 50% of the maximum effect and *Hill* is the slope parameter.

The model will be applied to the raw LSMean results (i.e. on the log_e-scale) from the primary MMRM model (Section 5.2.3) utilizing a Bayesian methodology approach with weakly informative priors as described in Appendix 2. Only the raw LSMean results from the placebo (combined Cohorts 1 & 2 only) and 1-week titration treatment groups (from Cohort 1) will be included in the model, i.e. the results from the 2-week and 4-week titration treatment groups and placebo from Cohort 3 will not be included.

Estimates of the model parameters of E_0 , E_{max} , ED_{50} and *Hill* and their 95% credible intervals will be produced.

The posterior medians and 90% credible intervals (5th and 95th percentiles of the relevant posterior distribution) will be reported for each target randomized dose (including Placebo) and their differences relative to placebo. These will all be presented on the %scale by back transforming modelled results. Both will be reported in tables and plotted in separate figures.

If convergence cannot be obtained or visual inspection of the data does not support a dose-response Emax relationship the following options will be considered in order: (1) assume the hill parameter is 1 and remove from the model (giving a 3-parameter dose-response Emax model); (2) utilize alternative priors to those provided in the appendix 2; (3) otherwise this Emax model will not be reported and alternative model structures may be investigated and the subsequent analyses may be included in the CSR with rationale for the eventual model selected.

PFIZER CONFIDENTIAL DMB02-GSOP-RF02 8.0 *Statistical Analysis Plan Template* TMF Doc ID: 98.03 Page 28 of 61

5.2.6. Emax Model (baseline interaction)

An additional 4-parameter dose-response Emax model will be used to characterize percent change from baseline dose-response relationships, assuming an interaction between baseline body weight and dose.

The model structure will be the same as Section 5.2.5.

The model will be applied to the raw LSMean results (i.e: on the log_e-scale) from individual MMRM models that have been applied to each treatment group separately. The MMRM models will include time, strata, baseline (on the log_e-scale) as a covariate and the baseline-by-time interaction with time fitted as a repeated effect and participant as a random effect. Only the raw LSMean results from placebo (combined Cohorts 1 & 2 only) and 1-week titration treatment groups (from Cohort 1) will be included in the model, i.e. the results from the 2-week and 4-week titration treatment groups and placebo from Cohort 3 will not be included.

An unstructured covariance matrix will be used to estimate the variances and covariance within participant across time points for each separate MMRM. If convergence is not obtained or model fit is not adequate, then other covariance structures will be investigated as necessary. The Kenward-Roger approximation will be used for estimating degrees of freedom for the model parameters.

The raw LSMean results from the separate MMRM models (placebo and standard titration treatment groups only, as above) will be calculated for the average baseline body weight (i.e. across all participants in the Estimand Set 1A) and then fitted with the Emax model above utilizing a Bayesian methodology approach with weakly informative priors as described in Appendix 2

Estimates of the model parameters of E_0 , E_{max} , ED_{50} and *Hill* and their 95% credible intervals will be produced.

The posterior medians and 90% credible intervals (5th and 95th percentiles of the relevant posterior distribution) will be reported for each target randomized dose (including Placebo) and their differences relative to placebo. These will all be presented on the %scale by back transforming modelled results. Both will be reported in tables and plotted in separate figures.

If convergence cannot be obtained or visual inspection of the data does not support a dose-response Emax relationship the following options will be considered in order: (1) assume the hill parameter is 1 and remove from the model (giving a 3-parameter dose-response Emax model); (2) utilize alternative priors to those provided in the appendix 2; (3) otherwise an Emax model (with a baseline interaction) will not be reported.

5.2.7. Cumulative Incidence Plots

Cumulative Incidence Plots will be produced based on the time to the event of interest (starting from the time of start of dosing on Day 1) for each treatment group separately and will be plotted on the same graph. This will be based on plotting the cumulative incidence function (with no competing risks), which will be presented as a % on the y-axis. No statistical testing for differences between treatment groups will be considered.

PFIZER CONFIDENTIAL DMB02-GSOP-RF02 8.0 *Statistical Analysis Plan Template* TMF Doc ID: 98.03 Page 29 of 61 Details of censoring are included in Section 6 and example SAS code is provided in Appendix 3.

5.3. Methods to Manage Missing Data

Details of efficacy data to be censored is described in Section 3.2.

For applicable continuous endpoints modelled with an MMRM, missing/censored values will be imputed as part of the analysis method.

For the analysis of safety endpoints, the sponsor data standard rules for imputation of BLQ values will be applied.

In all PK data presentations (except listings), concentrations below the limit of quantification (BLQ) will be set to zero. In listings BLQ values will be reported as "<LLQ", where LLQ will be replaced with the value for the lower limit of quantification (LLQ).

Where a dose has been administered on site and actual dose, frequency, planned dose, planned dose frequency, end date time and start date time are missing, these missing values will be imputed with the details of the dose planned as per the protocol.

5.3.1. Multiple Imputation

For summarizing the proportion of responses in body weight, all data from Estimand Set 1 will be included (i.e. all time points up to and including End of Treatment). A multiple imputation (MI) method will be implemented, using a multivariate imputation method by chained equations, which is still valid with an arbitrary missing data pattern. The model will include: treatment, baseline body weight and strata. Twenty sets of imputations of each missing value will be constructed from the MI method and the proportion of responses by treatment group will be determined with associated standard errors utilizing a normal approximation and will be combined using standard multiple imputation techniques proposed by Rubin⁸ to yield overall estimates. If there is more missing data in the study than anticipated, the number of imputation sets may be increased as required.

For logistic regression of body weight, all data from Estimand Set 1 will be included (i.e. all time points up to and including End of Treatment). The same imputed datasets as produced for the proportion of responses above will be utilized, where a Logistic Regression model (as described in Section 5.2.4) will be applied to each of the 20 imputed datasets separately. Parameter estimates of the log odds ratios for each treatment group relative to placebo will be combined using standard multiple imputation techniques proposed by Rubin⁸ to yield overall estimates of the log odds ratios and their associated standard errors will be used to create 90% confidence intervals on the log-odds scale. The log odds ratios and log odds 90% confidence intervals will be back transformed into odds ratios and associated 90% confidence intervals for final reporting.

